9.1 TREATMENT/INTERVENTION PLAN

9.2 Aromatase Inhibitor Administration

This clinical trial was initially comprised of two arms, one for BYL719 in combination with letrozole (Arm A), and another for BYL719 in combination with exemestane (Arm B). As of January 2014, the study is being amended to include two additional arms, and patients will no longer be enrolled onto Arms A or B. On Arm C, patients will receive intermittent BYL719 (7 days on, 7 days off) in combination with daily letrozole, and on Arm D, patients will receive intermittent BYL719 (5 days on, 2 days off) in combination with daily exemestane. Patients will be eligible for only one of the two arms, Arm C or Arm D, depending on which AI

(letrozole or exemestane) they were taking before study enrollment (i.e., a patient who was taking letrozole will continue to take letrozole, and a patient who was taking exemestane will continue to take exemestane). Patients will not be randomized to one of the two arms.

Letrozole or exemestane will be self-administered by the study patients orally once daily. . On days that patients are taking BYL719, aromatase inhibitor should be swallowed concomitantly with BYL719, or less than 5 minutes apart, at approximately the same time every day. The recommended time of administration is approximately 9 am (+/- 2 hrs). On a day of PK bloodwork, patients will take the scheduled dose in clinic. Treatment doses for each AI will be fixed at the established dose (see Table 9-1 below). There will be no dose escalation or dose reduction for letrozole or exemestane.

Table 9-1

Arm	AI dose	BYL719 schedule (dose per cohort)
A	Letrozole 2.5mg orally once daily	Days 1-28 of 28 day cycle
B	Exemestane 25mg orally once daily	Days 1-28 of 28 day cycle
C	Letrozole 2.5mg orally once daily	Days 1-7, 15-21 of 28 day cycle
D	Exemestane 25mg orally once daily	Days 1-5, 8-12, 15-19, 22-26 of 28 day cycle

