The two arms of the study will be monitored in tandem, and we have added an overall sequential global stopping rule to be applied as both expansion cohorts are accruing. We include this early stopping rule across both arms because the mechanism and toxicities of both AIs are known to be very similar. Our global stopping rule is based on repeated significance testing and serves as a global safety measure. We assume a grade 4 toxicity rate of 10% as acceptable and 35% as unacceptable. With these assumptions, if 2 of the first 5 patients, 3 of the first 10 patients, 4 of the first fifteen or 5 of 20 patients accrued experience a grade 4 toxicity, we will discontinue the entire study. With this rule, the probability of discontinuing the study if the true toxicity rate is 35% is .92. If the true toxicity rate is 10%, this probability is .10.

Likewise, if two different recommended phase II doses are determined in the separate arms, safety data will be reviewed with the primary investigator and Novartis, and we will determine how to move forward. Depending on the circumstances, we will consider reducing the dose of BYL719 in the unaffected arm of the trial, if felt to be appropriate to ensure patient safety.

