14.3 Expansion Phase

In the expansion portion of the study, 10 additional patients will be enrolled in each arm, Arm C and Arm D, in order to further define the safety and feasibility of BYL719 in combination with letrozole or exemestane at the established dose from the dose-finding phase, and to estimate the efficacy of this combination.

In order to help ensure that the DLT rate observed among the additional 10 patients in each arm is consistent with the DLT rate observed at the established dose from the dose-finding portion, the following decision rule will be implemented for each of the two study arms. If ≥ 4 DLTs are seen at any time in any one expansion arm, then it is likely that the safe and tolerable dose determined during the first portion of the trial is too toxic. The safety data will then be reviewed with the primary investigator and Novartis to determine how to move forward. Depending on the circumstances, we may consider de-escalating the dose of BYL719 to the next lower dose level and accruing 10 additional patients at that level. The probability of observing at least 4 patients with a DLT in the 10 additional patients is .28 if 1 of 6 patients were seen with a DLT in the dose-finding phase of the study. The probability of observing at least 4 patients with a DLT in the 10 additional patients is .09 if 0 of 6 patients were seen with a DLT in the dose-finding phase of the study.¹¹ The below table provides additional details on the probability of observing at least 1 to 9 patients with DLTs in the expansion cohort of 10 patients given that 0 or 1 patient in the initial dose-finding cohort of 6 patients had a DLT.¹¹

DLTs in dose-finding cohort	DLTs in expansion cohort								
	1 DLT (of 10)	2 DLTs	3 DLTs	4 DLTs	5 DLTs	6 DLTs	7 DLTs	8 DLTs	9 DLTs
0 (of 6)	0.59	0.33	0.18	0.09	0.04	0.02	0.01	<0.01	<0.01
1(of 6)	0.85	0.64	0.44	0.28	0.16	0.08	0.04	0.01	0.01

The two arms of the study will be monitored in tandem, and we have added an overall sequential global stopping rule to be applied as both expansion cohorts are accruing. We include this early stopping rule across both arms because the mechanism and toxicities of both AIs are known to be very similar. Our global stopping rule is based on repeated significance testing and serves as a global safety measure. We assume a grade 4 toxicity rate of 10% as acceptable and 35% as unacceptable. With these assumptions, if 2 of the

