first 5 patients, 3 of the first 10 patients, 4 of the first fifteen or 5 of 20 patients accrued experience a grade 4 toxicity, we will discontinue the entire study. With this rule, the probability of discontinuing the study if the true toxicity rate is 35% is .92. If the true toxicity rate is 10%, this probability is .10.

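### The global grade 4 stopping rule pools Arms C and D, so its .92 holds only if all 20 patients share a 35% rate; with one arm at 35% and the other at 10% it stops about .60 to .64 of the time under interleaved accrual, and it then stops both arms

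*Combined protocol and SAP*

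**What the plan says.** Section 14.3, repeated in Section 9.6, sets one grade 4 toxicity rule for the two expansion cohorts of 10 patients each. Its design rates are "We assume a grade 4 toxicity rate of 10% as acceptable and 35% as unacceptable". The trigger is two events at the first look, and the list of looks reads "first 5 patients, 3 of the first 10 patients, 4 of the first fifteen or 5 of 20 patients accrued experience a grade 4 toxicity,". The consequence of reaching any of them is "we will discontinue the entire study". The justification for counting across arms is "We include this early stopping rule across both arms because the mechanism and toxicities of both AIs are known to be very similar".

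The operating characteristics are given for a single true rate: "With this rule, the probability of discontinuing the study if the true toxicity rate is 35% is .92", and .10 if the true rate is 10%. No case with different rates in the two arms is shown.

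Table 9-1 gives BYL719 in Arm C on days 1-7 and 15-21, and in Arm D on "Days 1-5, 8-12, 15-19, 22-26 of 28 day cycle". Section 9.6 also provides for a safety review "if two different recommended phase II doses are determined in the separate arms". A separate rule applies to each expansion arm: 4 or more DLTs lead to a safety review by the investigator and the manufacturer. Section 4.0 records that, as of June 2015, Arm D was enrolling its expansion cohort and the Arm C expansion was on hold.

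**The concern.** The reason for pooling concerns the background drugs. The agent under test is BYL719, and its schedule differs between arms: 7 + 7 = 14 dosing days per cycle in Arm C and 4 × 5 = 20 in Arm D. The protocol treats schedule as a driver of toxicity (Section 3.7 builds the amendment on the timing of rash), and the primary objective asks for a dose for each schedule separately. The similarity of toxicity in Arms A and B was seen with both arms on the same daily schedule, so it does not show that Arms C and D share a rate.

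One schedule too toxic and the other acceptable is therefore a case that the rule should be described for. In that case the acceptable arm's patients dilute the count, so the toxic arm is stopped less often than .92 suggests. When the rule does fire it cannot single out an arm, so the acceptable arm is lost as well.

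**Working it through.** **Inputs.** Boundaries, 10% and 35% rates, and 10 patients per arm: Section 14.3. Schedules: Table 9-1. Accrual order in the expansion phase: not given, so it is an assumption and the full range is shown.

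**Method.** Exact recursion. Take the distribution of the cumulative grade 4 count after each block of five patients. At each look, remove the probability at or above the boundary (2, 3, 4, 5) and carry the rest forward. P(stop) is the sum of the removed parts. Checking after every patient against the same boundaries gives the same answer.

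**Step 1. Reproduce the printed figures (common rate, 20 patients).**
- First look at 35%: 1 − .65⁵ − 5(.35)(.65⁴) = 1 − .116 − .312 = .572.
- All looks at 35%: .572 + .206 + .096 + .051 = .924 (sum of unrounded terms). The printed .92 reproduces.
- All looks at 10%: .081 + .032 + .016 + .009 = .138. The printed .10 does not reproduce.
- Requiring strictly more than each boundary gives .796 at 35% and .028 at 10%, which matches neither printed figure. Reaching the boundary is therefore the intended trigger.

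**Step 2. One arm at 35%, the other at 10%, 10 patients each.** Same recursion with patient-specific rates.
- Alternating, toxic arm first. The first block has three patients at 35% and two at 10%. P(0) = .65³ × .9² = .222. P(1) = 3(.35)(.65²)(.81) + .65³ × 2(.1)(.9) = .359 + .049 = .409. P(2 or more) = .369. All looks: .369 + .116 + .104 + .049 = .637.
- Alternating, acceptable arm first: .258 + .189 + .078 + .079 = .604.
- Average over all 184,756 orders: .626.
- Extremes: .515 if the acceptable arm accrues entirely first, .794 if the toxic arm does.

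Every order falls below .92. In each, the acceptable arm is discontinued with the same probability.

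**Step 3. Only one arm accrues.** The looks at 15 and 20 are never reached. At 35%: .572 + .206 = .777. At 10%: .081 + .032 = .113.

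**Step 4. The same two boundaries applied within each arm.** Each arm has the Step 3 figures, whatever the other arm does.
- Both at 35%: at least one arm stops with 1 − (1 − .777)² = .95.
- Both at 10%: at least one arm stops with 1 − (1 − .113)² = .21.

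**Step 5. Per-arm and pooled rules both in force** (simulation, alternating accrual). A 35% arm stops with about .81 when the other is at 10%, and about .94 when both are at 35%. With both at 10%, a given arm stops with about .19.

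**Step 6. The per-arm DLT review.** P(4 or more of 10) is .486 if the DLT rate is 35%, .62 at 40% and .83 at 50%.

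**The case against.** Five points can be made for the plan.

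- **Pooling is deliberate, explained and described as a global safety measure.** That stands. A reader might infer that the .92 is a miscalculation. It is not; what is missing is the condition it rests on.
- **There is arm-specific protection.** A reader might infer that a single toxic arm has no check of its own. The documents do not support that: the DLT rule works per arm and provides for possible de-escalation. DLTs include many grade 3 and some lower-grade events, so an arm with 35% grade 4 toxicity could well have a higher DLT rate, and .486 should not be taken as the chance of detection. But a DLT must be at least possibly related and start in Cycle 1, so it is a different event, and the rule triggers a review and not a stop.
- **The .60 to .64 assumes interleaved accrual.** That stands. The remark in Section 14.2 that the arms accrue simultaneously concerns dose-finding. A reader should not take .62 as a fixed property of the rule; the range is .515 to .794.
- **With Arm C on hold, nothing is diluted.** That stands for the June 2015 status: the rule then already is 2 of 5 and 3 of 10 in Arm D. But the figure is then .78, so .92 does not describe that situation either. Section 1.0 also records that accrual closed at 51 patients, which limits any prospective benefit.
- **Mixed toxicity is not shown to be likely.** That stands too. Each dose is confirmed at no more than 1 DLT in 6, which an arm with a 35% DLT rate passes with .65⁶ + 6(.35)(.65⁵) = .32. Different doses would lead to a safety review with possible reduction in the other arm. Nothing in the documents shows that either arm had a 35% grade 4 rate or that a toxic arm was missed.

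**Conclusion.** The concern holds as a limitation of the rule and of how it is described. The .92 is correct for 20 patients at a common 35% rate and for nothing weaker. With one arm at 35% and the other at 10%, the stopping probability is .60 to .64 under alternating accrual, about 28 to 32 points lower, and .515 to .794 over all orders. The acceptable arm stops with it. With Arm D alone it is .78. The stated reason for pooling does not cover the difference in BYL719 schedule or a possible difference in dose. Separately, the 10% figure should read about .14, not .10.

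These results assume 10 patients per arm, independent patients, and the plan's own 35% and 10% as the two arms' rates. The per-arm DLT review reduces the practical risk by an amount the documents do not allow one to fix.

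**What to change.** In Sections 9.6 and 14.3:

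1. Apply the existing boundaries of 2 of the first 5 and 3 of 10 within each expansion arm. A trigger discontinues that arm and halts the other pending safety review, as Section 14.2 already does in dose-finding. State .78 at 35% and .11 at 10% per arm.
2. If the pooled rule is kept as a backstop, state that .92 requires both arms at 35% and all 20 patients. Print the one-arm-toxic figure with its range (.60 to .64 alternating; .515 to .794 over all orders), and change the 10% figure from .10 to about .14.

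**Gain.** With the other arm at 10%, the chance of stopping a 35% arm rises from about .63 to .78. The exception is an order close to toxic arm entirely first, where pooling already gives up to .794. The acceptable arm is discontinued on its own count with probability .11, although it may be halted for review.

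**Cost.** The change is wording and recomputed figures, with no extra patients or data. If per-arm rules replace the pooled rule, some arm stops falsely with about .21 when both are at 10% (.11 for a given arm), against .138 now. Each arm's own detection when both are at 35% is then .78 instead of .92, although at least one arm stops with .95. If both rules are in force, a given arm stops falsely with about .19. As accrual has closed, the immediate use is to correct the stated properties and to report the rule with its conditions.

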Subjects currently enrolled onto Arms A and B will continue on Arms A and B. They will be re-consented with the revised Arm A and B consents which will reflect our updated toxicity profile. In addition, planned secondary objectives for Arms A and B (evaluation of safety and toxicity, estimation of efficacy, pharmacokinetic studies) will continue, though the analyses will only be performed based on those subjects enrolled onto Arms A and B (dose-escalation) as no subjects will be enrolled onto Arms A and B dose-expansion.

As of January 2017, this trial is being amended to revise the restaging scans and clinic visit requirements for patients who have been receiving protocol therapy for greater than 75 weeks. At the time of this amendment (Amendment 13) this study has closed to patient accrual after enrolling a total of 51 patients.

[figure not shown]

The original study schema (for Arms A and B) is shown above, and the schema for Arms C and D is shown below. Rather than proceed further with the dose-finding phase or continue to the expansion phase for Arms A and B, we will proceed directly to the dose-finding phase for Arms C and D given toxicity concerns discussed below. For Arm C and Arm D, there will be a dose-finding phase and an expansion phase. When the recommended phase II dose of intermittent BYL719 in combination with letrozole or exemestane has been determined in the dose-finding phase, an additional 10 patients will be enrolled onto Arm C and Arm D in an expansion phase of the study. The purpose of the expansion phase is to further define the safety and feasibility of BYL719 in combination with letrozole or exemestane given on two intermittent schedules, at the recommended phase II dose, and to estimate efficacy.

Dose-escalation phase

Dose-expansion phase

Patients will be eligible for either Arm C or Arm D depending on which AI they were taking before study enrollment. For both the dose-finding phase and the expansion phase, patients may have stable or progressive disease on letrozole or exemestane, and BYL719 will be added.

A treatment cycle will consist of 28 days. The regimen will consist of BYL719 in combination with letrozole or exemestane administered orally each day. Patients will be on treatment until unacceptable toxicity or progression of disease. Treatment doses and schedule are shown below:

Arm	AI dose	BYL719 schedule (dose per cohort)
A	Letrozole 2.5mg orally once daily	Days 1-28 of 28 day cycle

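### The global stopping rule as printed discontinues the study with probability .14, not the stated .10, when the true grade 4 rate is the acceptable 10%

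*Combined protocol and SAP*

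**What the plan says.** Section 14.3 plans 20 expansion patients: "10 additional patients will be enrolled in each arm, Arm C and Arm D". For safety across the two arms it states that "we have added an overall sequential global stopping rule to be applied as both expansion cohorts are accruing". The reference rates are given directly: "We assume a grade 4 toxicity rate of 10% as acceptable and 35% as unacceptable". The boundaries appear in the same terms in Sections 9.6 and 14.3; Section 9.6 has "if 2 of the first 5 patients, 3 of the first 10 patients, 4 of the first fifteen or 5 of 20 patients accrued". Reaching any of them on grade 4 toxicity ends the entire study.

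Both sections then give two operating characteristics: a probability of .92 of discontinuing when the true rate is 35%, and, for the acceptable rate, "If the true toxicity rate is 10%, this probability is .10".

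Section 1.0 records, as of Amendment 13, that "this study has closed to patient accrual after enrolling a total of 51 patients".

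**The concern.** The first look alone suggests a problem. With a true rate of 10%, the chance of 2 or more events in 5 patients is already .081. Three further looks, each able to stop the study, leave less than .02 to spend if the total is to be .10.

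This figure is the plan's only statement of how often a mandatory rule would close the study at a toxicity rate the plan regards as acceptable. If it does not belong to the printed boundaries, then either the probability or a boundary is wrong. Anyone who reports the rule's properties from the plan would repeat the mismatch.

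**Working it through.** **Inputs** (Section 14.3, repeated in 9.6): looks at n = 5, 10, 15, 20 pooled patients; stop if the cumulative number with grade 4 toxicity is at least 2, 3, 4, 5 respectively; true rate p = .10 or .35. Patients are taken as independent with a common rate.

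**Method.** Patients arrive in blocks of 5. Within a block, P(k) = C(5,k) p^k (1−p)^(5−k). At each look, add the probability of crossing for the first time, then carry forward only the counts below the boundary.

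**The plan's .92 first (p = .35).** First-crossing probabilities are .5716, .2058, .0959 and .0505. They sum to .9238, so .92 is reproduced. This also supports the model and the reading of the boundaries as 'at least'.

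**The plan's .10 (p = .10).** One block gives P(0) = .59049, P(1) = .32805, P(2) = .07290, P(≥2) = .08146, P(≥3) = .00856, P(≥4) = .00046, P(5) = .00001.

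- *Look at 5.* Stop with probability .08146. Continue with 0 events (.59049) or 1 event (.32805).
- *Look at 10.* Stop: .59049 × .00856 + .32805 × .08146 = .00505 + .02672 = .0318. Continue with 0, 1 or 2 events: .34868, .38742, .15066. For example, the last is .59049 × .07290 + .32805² = .15066.
- *Look at 15.* Stop: .34868 × .00046 + .38742 × .00856 + .15066 × .08146 = .00016 + .00332 + .01227 = .0158. Continue with 0 to 3 events: .20589, .34315, .24148, .08049.
- *Look at 20.* Stop: .20589 × .00001 + .34315 × .00046 + .24148 × .00856 + .08049 × .08146 = .00000 + .00016 + .00207 + .00656 = .0088.

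| Look | Boundary | Cumulative stop, p = .10 | Cumulative stop, p = .35 |
|---|---|---|---|
| 5 | 2 | .0815 | .5716 |
| 10 | 3 | .1132 | .7774 |
| 15 | 4 | .1290 | .8733 |
| 20 | 5 | .1378 | .9238 |
| Stated | | .10 | .92 |

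The stated .10 is passed at the second look. Simulation agrees: 1,000,000 trials gave .1378 and .9239.

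**Could another reading give .10 with .92?**

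| Reading | p = .10 | p = .35 |
|---|---|---|
| More than 2, 3, 4, 5 | .028 | .796 |
| Looks at 5, 10, 15 only | .129 | .873 |
| Looks at 5 and 10 only | .113 | .777 |
| Single look at 5 | .081 | .572 |
| Single look at 10 | .070 | .738 |
| Single look at 15 | .056 | .827 |
| Single look at 20 | .043 | .882 |
| No look at 5, or 3 of 5 at that look | .0996 | .9151 |

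Checking after every patient is not a separate reading: counts cannot fall, so a boundary reached inside a block is still met at its end, and the result is again .1378.

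Only the last row rounds to the printed pair. A search over non-decreasing integer boundaries at 5, 10, 15 and 20 patients found no other set giving .10 (rounded) at 10% and a value within about two points of .92 at 35%. The two versions in that row are equivalent, because 3 events among the first 5 patients would also stop the study at the look at 10.

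**Rate that would give .10.** Solving the printed rule for a stopping probability of .10 gives a true grade 4 rate of 8.6%, not 10%.

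**The case against.** The arithmetic is not in dispute; the strongest objections concern what follows from it.

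- *The figure may be right and the boundary misprinted.* Because 3 of 5, or no look at 5, returns .0996 and .9151, the evidence shows only that rule and figure disagree. This stands. It is why .14 is attached to the rule as printed, and why the sponsor has to say which was meant.
- *The full 20 patients may never have applied.* Section 4.0 says that Arm C expansion was on hold as of June 2015. If it never resumed, which the documents do not say, only the looks at 5 and 10 could have operated, with probabilities .113 and .777. That matters for describing the trial as run. It does not rescue .10, and the plan presents its pair as design properties of the full rule.
- *Little hangs on it now.* Accrual has closed, the rule supports no efficacy inference, and the discrepancy lies on the side of stopping too readily. All true, and it limits the weight of the point. The stated number still does not describe the stated rule.
- *The relative excess is imprecise.* A printed .10 could stand for anything from .095 to .105, so the relative excess ranges from .1378/.105 = 1.31 to .1378/.095 = 1.45. Even at the upper rounding limit the gap is 3.3 points.

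**Conclusion.** The concern holds. For the boundaries printed in Sections 9.6 and 14.3, the probability of discontinuing the study at a true grade 4 rate of 10% is .138, against .10 stated: 3.8 percentage points, or 38% in relative terms. The .92 at 35% is correct.

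The result assumes independent patients with a common rate, 'at least' boundaries, and 20 pooled expansion patients if the rule is not met. The same assumptions reproduce the plan's .92. The documents do not settle whether the probability or the first boundary is the misprint. This should be corrected for accuracy; it does not weaken the stated protection at 35% and alters no remaining enrolment decision.

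**What to change.** The sponsor should establish from the design records which rule the printed probabilities were calculated for, and make Sections 9.6 and 14.3 agree.

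- If the printed boundaries are the intended rule, change .10 to .14 in both sections and leave .92 as it is.
- If .10 was the design target, reconcile the first-look boundary with it in both sections and state the pair of probabilities for the rule so confirmed. This review does not choose the boundary.

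Add that both figures assume all 20 pooled expansion patients. Any report of the rule's properties should say how many patients it was actually applied to.

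The cost is one figure, or one boundary, in two sections. No patients, data or analyses are affected. If the boundaries stand, the stated false-stop probability becomes slightly less favourable.
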